13.4 Analysis Plan

13.4.1 Analysis Populations.

Primary EHR data infant (PEDI) sample: All infants meeting inclusion/exclusion criteria for whom EHR data has been obtained at a 4-month or 6-month WCC in order to assess the primary endpoint of pediatric clinician adherence. Data regarding characteristics of the treating pediatric clinician are not required for an infant to be included in this population.

Secondary EHR data infant (SEDI) samples with pediatric clinician characteristics obtained: All infants meeting inclusion/exclusion criteria for whom EHR data has been obtained at a 4-month or 6-month WCC in order to assess the primary endpoint of pediatric clinician adherence and whose pediatric clinician has consented and completed the characteristics questionnaire information. In addition to characteristics obtained through the characteristics questionnaire information, data on completion of pre-study training for pediatric clinicians in the intervention arm will also be captured.

Exploratory EHR data infant (EEDI) samples

- With allergist adherence obtained (EEDI1): All high-risk infants meeting eligibility criteria who are referred to an allergist for testing and for whom data are obtained regarding the testing that was conducted, the outcome of the allergist testing and the recommendation provided by the allergist as to early introduction of peanut-containing food.
- With caregiver adherence obtained (EEDI2): All infants whose caregivers complete the FOABF and Caregiver Account of Clinician Peanut Recommendations, Testing and Introduction surveys at 12 and/or 24 months.

Pediatric clinician sample: All pediatric clinicians within the intervention group meeting consent and eligibility criteria who complete baseline and at least one follow-up knowledge, attitudes, or barriers and facilitators survey. Those clinicians in the control group will complete one follow-up knowledge, attitudes, or barriers and facilitators survey.

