13.4.2 Primary Analysis of Primary Endpoint(s)

The primary endpoint is the percentage of infants in the PEDI sample within each trial arm whose pediatric clinician adhered to the guidelines regarding peanut introduction. The primary

endpoint concerns peanut introduction recommendation by the treating pediatric clinician only and not additional behavior by the treating allergist or by caregivers.

The primary endpoint will be computed using EHR data from the 4-month and 6-month WCCs as follows:

For low-risk infants:

- Adherence is achieved if the pediatric clinician recommends introduction of peanut products.
- Non-adherence is achieved if the pediatric clinician fails to recommend introduction.

For high-risk infants, adherence is assessed through three routes. A pediatric clinician is adherent if:

- The pediatric clinician does not order an sIgE test and refers the infant to an allergist.
- The pediatric clinician does order an sIgE test, the result is ≤ 0.35 , and the pediatric clinician recommends introduction.
- The pediatric clinician does order an sIgE test, the result is > 0.35 , and the pediatric clinician refers the infant to an allergist.

A pediatric clinician is non-adherent if:

- The pediatric clinician does not order an sIgE test and does not refer the infant to an allergist.
- The pediatric clinician does order an sIgE test, the result is ≤ 0.35 , and the pediatric clinician fails to recommend introduction.
- The pediatric clinician does order an sIgE test, the result is > 0.35 , and the pediatric clinician does not refer the infant to an allergist.

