13.4.4 Analyses of Secondary and Other Endpoint(s)

Analysis of the secondary endpoint will be performed separately for high- and low-risk infants. Incidence of peanut allergy will be analyzed with generalized linear mixed models in the PEDI sample in the same manner as the primary pediatric clinician endpoint with infants as the unit of analysis.

Data for diagnosis of peanut allergy (yes/no) from the 4 month - 30 month EHR data collection time points will be combined into one binary variable describing whether (yes/no) diagnosis occurred at any time up through the 30-month time point. Data from caregivers FOABF surveys at 12 and/or 24 months will be used to determine the presence of a caregiver reported peanut allergy or physician diagnosed peanut allergy.

The peanut allergy endpoint will be determined by combining information from EHR and caregiver survey information as described in the MOP.

Exploratory analyses of the secondary peanut allergy endpoint will include the following. Analyses will be treated as exploratory and hypothesis- generating, so no formal correction for multiple testing will be applied.

- The primary analysis of the secondary endpoint will be repeated to evaluate the impact of missing data. Missing data will be classified in three ways as follows:
 - Missing data are not imputed via multiple imputation and are left missing.

- Missing data are imputed as non-peanut allergic.
- Missing data are imputed as peanut allergic.
- The primary analysis of the secondary endpoint will be repeated combining all infants from both the high- and low-risk groups. Risk group and the interaction of risk group and intervention group will be included as fixed effects predictors.
- The primary analysis of the secondary endpoint will be repeated in the PEDI sample including pediatric clinician adherence, allergist adherence (high-risk only), their interaction, and their interactions with intervention group as fixed effects predictors.
- The primary analysis of the secondary endpoint will be repeated in the EEDI2 sample including pediatric clinician adherence, allergist adherence (high-risk only), caregiver adherence, and all two- and three-way interactions with each other and intervention group, as fixed effects predictors.
- The primary analysis of the secondary endpoint will be repeated in the EEDI2 sample including the presence and extent (e.g., duration and amount) of peanut exposure as predictors.

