- A caregiver is adherent if the pediatric clinician and/or allergist's testing supports the introduction of peanut, and the caregiver introduces peanut products by 7 months of age and continues feedings with at least 6 g of peanut protein over ≥ 3 feedings per week as reported around the infant's 1st birthday ..
- A caregiver is adherent if the pediatric clinician and allergist's testing supports the avoidance of peanut and the caregiver does not introduce peanut products as reported around the infant's 1st birthday.
- A caregiver is *partially adherent* if the pediatric clinician and/or allergist's testing supports the introduction of peanut, and the caregiver introduces peanut products but does not do so by 6 months of age or does not continue feedings with at least 6 gm of peanut protein or over ≥ 3 feedings per week as reported around the infant's 1st birthday.
- A caregiver is non-adherent if the pediatric clinician and/or allergist's testing supports the avoidance of peanut, and the caregiver introduces peanut products as reported around the infant's 1st birthday.

The primary analysis of the exploratory endpoint will be repeated in the EEDI2 sample including pediatric clinician adherence, allergist adherence (high-risk only) and two-way interactions with each other and intervention group, as fixed effects predictors.

The primary analysis of the exploratory endpoint will be repeated in the EEDI2 sample by combining adherence and partial adherence and comparing partial and non-adherence.

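### In high-risk infants, the exploratory models that combine clinician and allergist adherence keep only referred infants, tie clinician adherence to sIgE status, and in EEDI2 carry too many terms to estimate

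*Combined protocol and SAP*

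**What the plan says.** Three exploratory models for high-risk infants enter clinician and allergist adherence together.

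- Section 13.4.4, peanut allergy in PEDI: "including pediatric clinician adherence, allergist adherence (high-risk only), their interaction, and their interactions with intervention group as fixed effects predictors".
- Section 13.4.4, peanut allergy in EEDI2: "including pediatric clinician adherence, allergist adherence (high-risk only), caregiver adherence, and all two- and three-way interactions with each other and intervention group".
- Section 13.4.5, caregiver adherence in EEDI2: "including pediatric clinician adherence, allergist adherence (high-risk only) and two-way interactions with each other and intervention group".

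Section 13.4.1 ties allergist adherence to EEDI1, which is "All high-risk infants meeting eligibility criteria who are referred to an allergist for testing", and further requires that the tests, their outcome and the allergist's recommendation were obtained. Neither a date limit for the referral nor a code for infants never referred is given.

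Section 13.4.2 defines clinician adherence from the 4- and 6-month visits. One adherent route is: "The pediatric clinician does not order an sIgE test and refers the infant to an allergist". The others are a negative sIgE with a recommendation to introduce, and a positive sIgE with referral. Infants who do not meet the criteria are set to non-adherent, and 13.4.3 names the test that is ordered but not carried out as the source of missing data. Section 8.2.2 extracts allergy visits up to 30 months of age. Sections 13.4.4 and 13.4.5 call these analyses exploratory.

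**The concern.** A predictor that exists only after referral is placed in samples that are not limited to referred infants. The fitted model then covers a different population from the one named. One full adherent route (negative sIgE, introduction recommended, no referral) is lost from it.

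Referral is also part of the definition of clinician adherence. Conditioning on it removes most ways of being non-adherent, and those that remain depend heavily on a negative test. A negative sIgE presumably marks lower peanut-allergy risk, so the coefficient would partly measure sIgE status. These are the plan's only models relating both clinician and allergist adherence to peanut allergy. A misleading coefficient could be read as evidence about the guideline itself.

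**Working it through.** **1. Nearest figure in the plan.** The plan gives no figure for these models. The closest is section 13.7: more than 80% power for 5.4% against 13.8% in high-risk infants. With 30 practices of 17 infants (255 per arm) and ICC 0.02, the design effect is 1 + 16 × 0.02 = 1.32. A two-sided 0.05 test then has power 0.80, so the figure reproduces. I use 500 infants and 13.8% below.

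**2. Enumeration of the rules in 13.4.2 and 13.4.3**

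| sIgE at 4/6 months | Not referred | Referred |
|---|---|---|
| Not ordered | non-adherent | adherent |
| Positive | non-adherent | adherent |
| Negative, introduction recommended | adherent | adherent |
| Negative, not recommended | non-adherent | non-adherent |
| Ordered, never run | non-adherent (imputed) | non-adherent (imputed) |

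Only the right-hand column can have an allergist-adherence value if referral means referral at these visits. Non-adherence there comes only from the last two rows.

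**3. Apparent effect when adherence has none.** All rates in this step except 500 and 13.8% are assumptions, not in the documents. sIgE is ordered in 40%, 10% of the orders are never run, and 20% of results are positive. Allergy risk is 40% if positive, so (0.138 − 0.2 × 0.4)/0.8 = 7.25% if negative, and 13.8% if untested. Referral: untested 50%, positive 80%, not run 30%. Of negatives, 60% get a recommendation (10% of these referred) and 40% do not (20% referred).

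- Counts: 300 untested, 20 not run, 36 positive, 144 negative.
- Adherent and referred: 150 + 28.8 + 8.64 = 187.4. Events: 20.7 + 11.52 + 0.63 = 32.8. Risk 17.5%.
- Non-adherent and referred: 11.52 negative + 6 not run = 17.5. Events: 0.84 + 0.83 = 1.66. Risk 9.5%.
- Odds ratio = (0.175/0.825)/(0.095/0.905) ≈ **2.0**.
- The fit uses about 205 of 500 infants. Among those dropped are 144 × 0.6 × 0.9 ≈ 78 who were adherent through a negative test and a recommendation.

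Other inputs move this widely. With sIgE ordered in 20% and only 10% of unrecommended negatives referred, it is about 1.5 (risks 15.4% and 10.6%, about 6 non-adherent infants). With no unrun tests, 25% positive and 50% risk if positive, it is about 15 (risks 20.5% and 1.7%, 12 non-adherent infants). These are cases, not bounds.

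**4. Later referrals.** EEDI1 does not exclude infants referred after 6 months. In the base case, 150 untested and 7.2 positive infants are unreferred and non-adherent. Suppose a share is referred later, with an assumed 30% allergy risk:

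| Referred later | Non-adherent in EEDI1 | Risk | Odds ratio |
|---|---|---|---|
| 0% | 17.5 | 9.5% | 2.0 |
| 5% | 25.4 | 15.8% | 1.13 |
| 10% | 33.2 | 19.2% | 0.89 |
| 20% | 49.0 | 22.7% | 0.73 |

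The sign turns at about 7%.

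**5. Size of the EEDI2 peanut-allergy model.** Arm, clinician, allergist and caregiver adherence give 4 main effects, and "and all two- and three-way interactions with each other and intervention group" gives 6 + 4 more: 14 coefficients, before the intercept and practice-volume terms. At most 500 × 0.138 = 69 events are expected, or 69/14 = 4.9 per coefficient. If half the infants are referred with data and half of those are surveyed (assumed), there are 125 infants and 125 × 0.138 ≈ 17 events, or 1.2 per coefficient.

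I simulated the fixed-effects part with 125 infants, 13.8% risk, 70% allergist adherence and 50% caregiver adherence (assumed). Separation or rank deficiency occurred in at least 298 of 300 datasets at every clinician non-adherence rate tried, from 2% to 20%. The 13.4.4 model labelled PEDI, taken as 6 coefficients in 250 referred infants, failed in roughly 98%, 84%, 57% and 36% of datasets at 2%, 5%, 10% and 13% non-adherence.

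**The case against.** The strongest reply is that these analyses are exploratory, that EEDI1 is openly defined, and that 13.4.6 tabulates every infant sample by risk group, so a reader would see the shrinkage. This stands in part. No primary or main secondary result depends on these models, and the low-risk versions have no allergist term. But tabulating the samples does not say which infants a model labelled PEDI or EEDI2 used. The expert adjudication in section 3.5 covers missing data elements, not infants never referred.

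Several stronger readings are tempting and are not supported.

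- **That the models cannot be fitted at all.** The 13.4.4 model labelled PEDI can often be fitted to complete cases. It then answers a narrower question in a selected group.
- **That adherence will look harmful.** This is likely if referral is confined to the 4- and 6-month visits. The documents do not confine it, and step 4 shows that the sign can reverse.
- **That non-adherent referred infants are almost all sIgE-negative.** Tests never run also count. With 20% of orders unrun and 25% of results positive, negatives are 120 × 0.4 × 0.2 = 9.6 of 9.6 + 40 × 0.3 = 21.6, or 44%.
- **That the harm argument reaches section 13.4.5.** The outcome there is caregiver adherence. Only the sample mismatch and the restricted clinician variable carry over.

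It can also be said that 17 events understates the count, because referral favours higher-risk infants. That is fair. In the base case, referred infants have 34.5/205 = 16.8% risk, which gives about 21 events, still only 1.5 per coefficient.

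**Conclusion.** The concern holds in this form. The sample mismatch and the link between clinician non-adherence and sIgE follow from the plan's own definitions and need no assumed figure. The size and direction of the bias do need assumptions. With no true effect, the illustrated odds ratios run from about 1.5 to about 15 if referral is limited to the 4/6-month window, and to 1 or below once enough later, symptom-driven referrals enter. The non-adherent group is small, about 6 to 18 infants in the cases in step 3. A coefficient whose sign depends on an unstated window cannot be interpreted.

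The EEDI2 peanut-allergy model is very likely inestimable: 14 coefficients, at most 4.9 events each, and probably nearer 1. The matter deserves correction because the plan, followed as written, gives a selected and confounded estimate. It does not touch the trial's main conclusions.

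**What to change.** For high-risk infants in 13.4.4 and 13.4.5, replace the joint clinician and allergist adherence terms, and their interactions, by one pathway variable that is mutually exclusive and exhaustive. Build it from:

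- sIgE status at the 4/6-month visits: not ordered, ordered but not run, negative, positive;
- clinician action: introduction recommended or not, referred or not;
- for referred infants, allergist adherence: adherent, non-adherent, no data.

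Collapse sparse cells by a rule stated in advance, keeping sIgE status separate from referral so that untested and sIgE-positive infants are not pooled. Count referral only in the window used for clinician adherence. Report peanut allergy and caregiver adherence by pathway and arm, without the two- and three-way interactions, labelled as association.

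If a model with allergist adherence is kept, name EEDI1 (or its overlap with EEDI2) as its sample, omit the clinician-adherence term and adjust for sIgE status.

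The cost is SAP wording, with no new data and no change to the sample size. The exploratory adherence interactions would no longer be estimated.

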13.4.5 Analyses of Exploratory Endpoint(s)

All analyses will be provided separately for high- and low-risk groups as noted. The entire infant sample of both risk groups will also be analyzed together where noted. Analyses will be treated as exploratory and hypothesis- generating, so no formal correction for multiple testing will be applied.

Allergist adherence will be analyzed with generalized linear mixed models for high-risk infants in the EEDI1 sample in the same manner as the primary pediatric clinician endpoint with infants as the unit of analysis. The allergist adherence endpoint will be determined as follows:

An allergist is adherent if:

- The allergist recommends introduction following a sIgE test ≤ 0.35 , a skin prick test 0-2mm, a successful supervised feeding or a successful oral graded food challenge.
- The allergist recommends avoidance and continued monitoring after a skin prick test ≥ 8 mm or a failed supervised feeding or oral graded food challenge.

An allergist is non-adherent if:

- The allergist fails to recommend introduction following a sIgE test ≤ 0.35 , a skin prick test 0-2mm, a successful supervised feeding or a successful oral graded food challenge.
- The allergist recommends introduction following a skin prick test 3-7mm without performing a supervised feeding or oral graded food challenge.
- The allergist recommends introduction following a skin prick test of ≥ 8 mm.

Caregiver adherence (yes/no) will be analyzed with generalized linear mixed models in the EEDI2 sample in the same manner as the primary pediatric clinician endpoint with infants as the unit of analysis. Only high risk infants with data on clinician and/or allergist testing will be used in the analysis of caregiver adherence. For the high risk infants in the primary analysis of the exploratory endpoint, partial caregiver adherence (as defined below) will be grouped with non-adherence. The caregiver adherence endpoint will be determined as follows:

For low-risk infants:

- A caregiver is adherent if the caregiver introduces peanut by 12 months of age, regardless of the pediatric clinician's recommendation.
- A caregiver is non-adherent if the caregiver does not introduce peanut by 12 months of age, regardless of the pediatric clinician's recommendation.

For high-risk infants:

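### The exploratory models of peanut allergy on feeding duration and amount, and on high-risk caregiver adherence, do not stop a reaction that ends feeding from lowering the exposure measure

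*Combined protocol and SAP*

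**What the plan says.** Section 13.4.4 defines the secondary outcome as one yes/no variable for whether "diagnosis occurred at any time up through the 30-month time point", supplemented by the caregiver surveys. Two of its exploratory repeats, both in the EEDI2 sample, put feeding behaviour on the right-hand side. One enters "caregiver adherence, and all two- and three-way interactions with each other and intervention group, as fixed effects predictors". The other "will be repeated in the EEDI2 sample including the presence and extent (e.g., duration and amount) of peanut exposure as predictors". Neither states a lag, a landmark age, or a cut-off of exposure at the first reaction or diagnosis.

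Section 13.4.5 defines caregiver adherence by three rules:

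- **High-risk, tests support introduction:** the caregiver introduces by 7 months and "continues feedings with at least 6 g of peanut protein over ≥ 3 feedings per week as reported around" the first birthday. A caregiver who "introduces peanut products but does not do so by 6 months of age or does not continue feedings with at least 6 gm", or falls short on frequency, is partially adherent. No category covers stopping after a reaction.
- **High-risk, tests support avoidance:** the caregiver is adherent if "testing supports the avoidance of peanut and the caregiver does not introduce peanut products as reported around" the first birthday.
- **Low-risk:** introduction by 12 months is enough. There is no amount, frequency or continuation rule.

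For the main analysis of the caregiver-adherence endpoint, "partial caregiver adherence (as defined below) will be grouped with non-adherence". Section 13.4.4 does not say how partial adherence enters the allergy model.

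**The concern.** Peanut allergy shows itself through a reaction, and a reaction usually ends feeding. Take an infant introduced at 6 months who reacts at 8 months and stops. That infant counts as allergic, and also has short duration and low total amount. If high-risk on the introduction route, the infant is partially adherent because the caregiver "does not continue feedings with at least 6 gm of peanut protein or over ≥ 3 feedings per week". The outcome has come first and set the predictor. Allergic infants then collect among the short-duration, low-amount and not-fully-adherent, even if feeding has no effect on allergy.

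These are the only planned models that relate how long and how much peanut was fed to whether allergy developed. A protective dose-response in them would be an attractive finding, and as specified it could not be told apart from this artefact.

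**Working it through.** The plan gives no effect size or power for these models, so there is no stated figure to reproduce. The check asks what odds ratio (OR) they would return if feeding had no effect.

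**Inputs from the documents.** Peanut allergy incidence p is 13.8% in high-risk and 1.5% in low-risk infants; about 500 high-risk and 10,000 low-risk infants are expected (both Section 13.7).

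**Assumptions, not in the documents.** a = share who would meet the feeding rule in the absence of a reaction. s = share of the allergic infants among them who react and stop before the assessment.

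**1. High-risk, introduction route.**

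- Risk in continuers = p(1−s) / [p(1−s) + (1−p)]
- Risk in others = p[1−a(1−s)] / {p[1−a(1−s)] + (1−p)(1−a)}
- OR = odds[a(1−s)] / odds[a]

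For a = 0.5 and s = 0.5, continuers have 0.069/(0.069 + 0.862) = 7.4% and others 0.1035/(0.1035 + 0.431) = 19.4%. The OR is (0.25/0.75)/(0.5/0.5) = 0.33.

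| a | s | Continuers | Others | OR |
|---|---|---|---|---|
| 0.3 | 0.3 | 10.1% | 15.3% | 0.62 |
| 0.5 | 0.3 | 10.1% | 17.2% | 0.54 |
| 0.5 | 0.5 | 7.4% | 19.4% | 0.33 |
| 0.5 | 0.7 | 4.6% | 21.4% | 0.18 |
| 0.7 | 0.7 | 4.6% | 29.7% | 0.11 |

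The OR does not depend on p. The absolute risks do, and 13.8% is for all high-risk infants, not only those whose tests support introduction.

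**2. Low-risk, duration and amount.** The same formulas apply to continuing versus stopping. With p = 1.5%, a = 0.6 and s = 0.5, continuers have 0.76% and others 2.60%. The OR is (0.3/0.7)/(0.6/0.4) = 0.29.

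**3. Predictors that stopping does not change.** Low-risk caregiver adherence is fixed once peanut is introduced, so this mechanism gives an OR of 1. The same holds for presence of exposure. In a null simulation of 2,000,000 infants (70% introduced, 40% stopping for other reasons, s = 0.5, 13.8% incidence), the OR was 0.37 when exposure required continued feeding and about 1.00 for introduced yes/no.

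**4. High-risk adherence with the avoidance route included.** Let v = share on that route and pv = allergy risk among them, with 90% avoiding, a = 0.6, s = 0.5 and total incidence 13.8%. For v = 0.10 and pv = 0.5, introduction-route risk is (0.138 − 0.05)/0.9 = 0.0978.

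- Adherent and allergic: 0.9 × 0.0978 × 0.3 + 0.1 × 0.5 × 0.9 = 0.0714
- Not adherent and allergic: 0.138 − 0.0714 = 0.0666
- Adherent, not allergic: 0.9 × 0.9022 × 0.6 + 0.1 × 0.5 × 0.9 = 0.5322
- Not adherent, not allergic: 0.862 − 0.5322 = 0.3298

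OR = (0.0714/0.0666)/(0.5322/0.3298) = 0.66.

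| v | pv = 0.5 | pv = 0.9 |
|---|---|---|
| 0.05 | 0.44 | 0.65 |
| 0.10 | 0.66 | 1.47 |
| 0.15 | 1.00 | 5.12 |

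The last cell is extreme: it places 0.15 × 0.9 = 0.135 of the 0.138 total on the avoidance route. The direction of the combined coefficient is not fixed.

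**5. Which remedy works.** A second null simulation assumed introduction at 5-7 months, 40% stopping for other reasons, and reactions spread evenly up to 12 months.

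| Exposure definition | s = 30% | s = 50% | s = 70% |
|---|---|---|---|
| Duration cut off at first reaction, ≥4 months vs less | 0.52 | about 0.35 | 0.23 |
| Landmark at 9 months | 0.94-0.98 across the three values | | |
| Age at introduction | 1.00 | 1.00 | 1.00 |

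Cutting exposure off at the reaction fails because the reaction still ends the count. The landmark removes most of the bias, though not necessarily all: if reactions occur only while an infant is being fed, dropping early reactors still thins allergic infants from the longer-fed group.

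**The case against.** The strongest reply is that 13.4.4 calls these analyses exploratory and hypothesis-generating, the randomised comparisons do not use these predictors, and 13.4.6 separately reports reactions at first and later exposures. That limits the consequence. But the label is given as the reason for not correcting for multiple testing, and it does not deal with a systematic bias. Counting reactions does not adjust the model.

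A reader might infer several stronger things that the documents do not support:

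- **That caregiver adherence as a whole is affected.** It is not. The low-risk rule, covering about 10,000 of 10,500 expected infants, has no continuation requirement.
- **That the models must show protection.** For high-risk adherence they need not. On the avoidance route adherence means not introducing, which pushes likely-allergic infants into the adherent group.
- **That extent requires feeding to about 12 months.** No such rule is written. Stopping simply shortens duration and lowers amount.
- **That the allergy model counts partial adherence as non-adherence.** That grouping is stated only where caregiver adherence is the outcome. For that endpoint 13.4.5 also plans a repeat that joins partial with full adherence, which partly meets any complaint about scoring a caregiver who stopped.
- **That the artefact matches the 81% reduction quoted in Section 1.1.** Some assumed values of a and s come close. That is a product of the values chosen and carries no evidential weight.

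**Conclusion.** The point holds in a limited form. The duration-and-amount model in both risk groups, and the caregiver-adherence predictor for high-risk infants whose tests support introduction, are open to reverse causation, and nothing in 13.4.4 or 13.4.5 prevents it. On the introduction route the spurious OR is 0.62 to 0.11 over a and s of 30-70%. Those fractions are assumptions, so the range shows how sensitive the models are and does not forecast a result. For high-risk adherence with both routes combined, neither size nor direction can be stated. Low-risk caregiver adherence, presence of exposure and the comparisons by arm are not touched by this mechanism. The Manual of Procedures, which holds the allergy algorithm, is not among the documents.

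This is a worthwhile, low-cost correction to exploratory analyses. It is not a threat to the trial's main conclusions.

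**What to change.** In 13.4.4:

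- Replace the whole-period exposure predictors with a landmark analysis: exposure and caregiver feeding up to a pre-stated age, in infants with no peanut reaction or allergy diagnosis by that age, with allergy counted afterwards.
- Report age at introduction as a supporting predictor, noting that it can itself be affected when a diagnosis or positive test prevents introduction.
- Do not simply truncate exposure at the first reaction.
- State how partial adherence enters the allergy model. Sections 13.2 and 13.4.5 also differ on its age limit (7 versus 6 months) and must be reconciled.

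In 13.4.5, tabulate separately caregivers who introduced on time and stopped after a reported reaction or diagnosis. This is an analysis category only and implies no view on feeding.

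The cost is SAP wording and derivation work. Section 3.5 and Tables 8.1 and 8.2 already list timing, amount and frequency of feeding, reactions, and dates of visits and tests. The questionnaires are not in the documents, so the team should confirm that reactions can be dated well enough for the chosen landmark. Infants with events before the landmark are dropped, so these exploratory estimates become less precise.
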